## Methods and Material

### Study design

To address the aim of the study, an open-label, randomised controlled trial (RCT) will be conducted, as well as a qualitative interview.

Participants will be allocated in a 1:1:1 ratio to either: treatment as usual by a general practitioner (TAU-GP), treatment as usual by a psychologist (TAU-P) in the form of cognitive

behavioural therapy (CBT), or an algorithm-based medical treatment by a general practitioner (ALGO). The duration of the study is up to 14 weeks, with 12 weeks of treatment and up to 2 weeks between screening and baseline. Participants will be evaluated at baseline, 4 weeks, 8 weeks and 12 weeks after baseline, respectively. For all 3 arms, an external rater will carry out the Hamilton Depression Rating Scale (HAM-D) screening.

The study design and duration are illustrated in Figure 1.

[figure not shown]

Figure 1: Study Design (GP: General practitioner. TAU: Treatment as usual. PSE: Present State Examination).

### Study intervention

In the two treatment as usual arms (TAU-GP and TAU-P), the choice of treatment and the frequency of patient consultations are at the discretion of the general practitioner (GP) and the psychologist. However, the psychologist will utilize cognitive behavioural therapy (CBT) as part of the treatment approach.

In the TAU-GP arm, the GP's can refer patients for psychotherapy, if deemed necessary, after initiation of medication. In the TAU-P arm, the psychologist may request initiation of medication through the general practitioner after psychotherapy, in the form of cognitive behavioural therapy (CBT), has been initiated.

For the algorithm-based treatment arm (ALGO), the GP drafts an individual, algorithm-guided stepped-care plan that merges measurement-based care with pre-set critical decision points (see figure 2). Every 2–4 weeks, validated symptom scores and side-effects are reviewed against evidence-based thresholds. Symptom scale score results are conveyed as “if-then” rules, triggering the next action, e.g. dose optimisation, switch, augmentation, or psychologist referral, as defined at baseline. These structured checkpoints prevent therapeutic drift and ensure the treatment keeps advancing until meaningful improvement is achieved, while still leaving room for clinical judgement and patient preference. The plan is based on the patient’s symptoms, previous treatment history, current clinical guidelines, possible side effects to antidepressants and the general practitioner’s clinical assessment.

The choice of treatment will follow predetermined steps, and the algorithm will include critical decision points (CDPs) at weeks 4, 8 and 12, where treatment efficacy is assessed. This assessment will lead to specific and predetermined adjustments regarding the current treatment (e.g. to continue current treatment or to change choice of treatment from the predefined plan) and in relation to preset “if-then” rules.

[figure not shown]
As a result of lack of tolerability to the current treatment, an earlier switch to an alternative treatment will be possible. In such cases, the algorithm will continue from that point, with a new HAM-D6 measurement conducted four weeks later.

Figure 2 illustrates the baseline measurement of HAM-D6, followed by initial treatment, and subsequent HAM-D6 measurements and treatment decisions at weeks 4 and 8.

Figure 3 illustrates the patient’s course in the ALGO group, including consultations in general practice, where the GP follows the algorithm-based treatment strategy, and study visits with the investigator or study staff during which ratings are conducted.

Supportive consultations with the participant’s general practitioner will continue as part of the usual care and are available to participants in all three treatment arms. The protocol exclusively evaluates the defined pharmacological strategies; other clinical interventions, including supportive consultations in accordance with current guidelines, are not restricted by the study.

Additionally, following randomisation, a random sample of 20% of the participants from each of the three treatment arms will be invited to a semi-structured diagnostic interview using Present State Examination (PSE) to elucidate the diagnostic accuracy of the diagnosis of depression made by the GPs and to investigate further comorbidities. The participants will be selected at baseline, but the diagnostic interview will be carried out after end of study week 12. In figure 1, the selection of 20% of the participants is illustrated with a dashed box beneath baseline, including that the diagnostic interview (PSE) will be carried out after 12 weeks.

**Figure 2: Treatment algorithm:** A) Illustrates the measurements, treatment strategies, and critical decisions points. B) Visualises the steps used for each measured HAM-D6 score after baseline.

[figure not shown]

Figure 3: Patient's course in the ALGO group.

### Randomisation

Patients will be allocated to one of the three arms by randomisation in a 1:1:1 ratio. At least 57 patients are required in each group, including an estimated dropout of 20%, to detect a clinically relevant difference as outlined in the Statistics section.

The randomisation sequence is coded by a single programmer with random block sizes of 3, 6 and 9 participants and with the randomisation sequence stored in REDCap (Research

Electronic Data Capture, Vanderbilt University), thus ensuring inaccessibility to all clinicians using the REDCap module for the randomisation of patients.

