## Patient Population

### Study population

Participants will include patients from general practice diagnosed with unipolar depressive disorder by a general practitioner, in which there is clinical uncertainty as to which of the initial treatments (medication or psychotherapy) would be most beneficial. Patients will be aged 18 to 65 at baseline.

Participants will be recruited from multiple general practices in the North Denmark Region by their general practitioner. 171 participants will be included with an expected dropout rate of 20%.

Symptomatic remission (i.e. remitters) is evaluated using the Hamilton Rating Scale for Depression, 6 item version (HAM-D6) and is defined as a score  $\leq 5$  (20). Symptomatic response (i.e. responders) is also evaluated using the HAM-D6 and is defined as a 50% reduction in the HAM-D6 score. For further details, see figure 2.

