#### [Exclusion criteria](#)

1. Misuse of substances that might influence the study, as judged by the investigator.
2. Difficulty in understanding the Danish language, as judged by the investigator.
3. A diagnosis of dementia.
4. Medical conditions that might interfere with the study outcome or safety, judged so by the investigator.
5. Pregnancy.
6. High risk of non-adherence at the investigator's discretion.
7. Suicidality: according to C-SSRS with a positive response to question 4 or 5 within the last three months or upon investigator's discretion.
8. No current medical or psychotherapy treatment initiated within the last 4 weeks prior to screening.

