## [Recruitment and Information](#)

### [Recruitment of study participants](#)

Recruitment will solely take place from general practices in the North Denmark Region by general practitioners, and participants will be recruited from among their patients.

All eligible patients will be informed that participation in the study is voluntary and a refusal to participate will not affect their treatment in any way. Further, they are informed that, if choosing

to participate, they can withdraw their consent at any given time during the trial. This information will be given by the investigator.

When a general practitioner has found a patient eligible for inclusion into the study, the GP can refer the willing, potential participant to the investigator or study staff for further information regarding the study and for possible participation. An oral acceptance is obtained by the GP, permitting the investigator to contact the potential participant through telephone (pre-screening) to set up a time for the screening visit. The written information about the study will be sent prior to the screening visit but will be discussed during the visit regardless. Inclusion and screening are carried out by the investigator during a physical meeting (screening visit) with the participant. When informed consent has been acquired, baseline interview and ratings can commence. During the screening visit, the participants will receive both the informed consent form as well as oral and written information about the study.

Screening visits for eligibility in the trial as well as virtual meetings can be delegated to a research assistant if deemed competent by the investigator.

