## Flowchart of Participant's Course

## Table of Measurements

Week	-2 to -1 Screening	0 Baseline	4	8	12 End of Study	Un-scheduled visit
Meeting form	In person	Virtual meeting	Virtual meeting	Virtual meeting	Virtual meeting	Virtual meeting
Signed Consent Form	X					
Inclusion and exclusion criteria	X					
Oral + written information	X					
Randomisation	X					
Adverse events		X	X	X	X	X
Demographic data	X					
Rating Scales						
HAM-D6		X	X	X	X	X
C-SSRS	X	X	X	X	X	X
PSP		X	X	X	X	
DART		X				
PSE						X*
Self-report forms						
MDI		X	X	X	X	
Brief INSPIRE-O		X	X	X	X	

HAM-D6: The Hamilton Depression Scale, item 6.

C-SSRS: The Columbia-Suicide Severity Rating Scale.

PSE: Present State Examination.

MDI: Major Depression Inventory.

PSP: The Personal and Social Performance Scale.

DART: The Danish Adult Reading Test.

\*In person

All visits and phone calls are scheduled within the defined time frame +/- 3 days. Pre-screening is conducted by a phone call by the investigator or study staff. The written study information will be sent in advance of the screening visit, and if the patient prefers, the letter of consent will also be sent prior to screening. The screening visit is a physical meeting where oral and written information is presented, and written consent can be obtained. Should the patient wish to, they can have at least 24 hours and no more than a week to consider the consent form. A follow-up meeting will be scheduled.

If, during the screening visit, the patient is found to meet all criteria for trial participation, the first treatment visit (baseline visit) will be scheduled within 14 days of the screening. The patient is randomised to treatment at screening.

A virtual baseline meeting is scheduled with the investigator or a competent research assistant. Study visits (virtual meetings) at 4, 8 and 12 weeks, as well as potential telephone calls, are scheduled with the investigator or study staff. Both screening and baseline visits are study related.

Table 1 further visualises the duration of time of each rating scale and interview as well as type of the rating scale, along with the duration of time and type for the different kinds of visits.

	Duration	Type
C-SSRS	1. visit 20 minutes (hereafter 5 minutes)	Rating scale - Interview
PSP	15 minutes	Rating scale - Interview
DART	5 minutes	Rating scale - Interview
HAM-D6	15 minutes	Rating scale - Interview
PSE	60-90 minutes	Semi-structured interview

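### Small permuted blocks on what appears to be one unstratified list make the next arm guessable about 55% of the time in this open-label trial, an avoidable opening for selection bias

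*Protocol*

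**What the plan says.** - **Allocation (Protocol, Randomisation).** "Patients will be allocated to one of the three arms by randomisation in a 1:1:1 ratio". "The randomisation sequence is coded by a single programmer with random block sizes of 3, 6 and 9 participants". The sequence is stored in REDCap, "thus ensuring inaccessibility to all clinicians using the REDCap module for the randomisation of patients". No stratification factor is named. Centre appears only as a random effect in secondary models (Statistics).
- **Blinding (Study design).** "an open-label, randomised controlled trial (RCT) will be conducted".
- **Who decides on entry (Recruitment of study participants).** "Inclusion and screening are carried out by the investigator during a physical meeting (screening visit) with the participant". The task may be delegated to a research assistant.
- **When (Table of Measurements).** "The patient is randomised to treatment at screening". The investigator or study staff also hold the visits at weeks 4, 8 and 12.
- **Discretionary items (Exclusion criteria).** Substance misuse, language, medical conditions and suicidality involve the investigator's judgement, as does the item that begins "High risk of non-adherence at the investigator".
- **Disclosure (Publication of Results).** The protocol, which prints the block sizes, is to be published.

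**The concern.** Concealing the future list is necessary, but in an open-label trial it is not sufficient. Every completed block brings the three arm totals back to equality. The arm that is behind at any moment is therefore more likely to come next, and a running tally is enough to see which arm that is.

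The team that judges eligibility is also the team around which treatment is openly known. If it expects a particular arm, it could decline or defer a borderline candidate, consciously or not. The arms would then differ in prognosis before treatment starts, and the bias would enter the primary F-test and the ALGO contrasts. The external HAM-D6 rater gives no protection, because this bias acts on who enters. The stated hypothesis favours ALGO, so the direction of any leaning is foreseeable.

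**Working it through.** **Inputs from the protocol.** Three arms, 1:1:1; blocks of 3, 6 and 9 (Randomisation); 171 patients and 20% dropout (Study population); SD of change 3.9 and difference 2.25 (Power calculation). The mix of block sizes is not given, so equal probability is assumed and the range over all mixes is shown.

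**The plan's own figure.** The protocol gives no predictability figure. Its sample size reproduces: a three-group F-test with one arm 2.25 points apart, SD 3.9 and 45 per group has power 0.805. Then 45/0.8 = 56.25, rounded up to 57, and 3 × 57 = 171.

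**Guess rate.** The rule is to name the arm with the fewest allocations so far, with ties broken at random. Totals are equal at each block start, so this equals naming the arm with most places left in the block. The block boundaries need not be known. Expected correct guesses per block:

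| Block size | Correct guesses | Rate |
|---|---|---|
| 3 | 1/3 + 1/2 + 1 = 1.833 | 61.1% |
| 6 | 3.367 | 56.1% |
| 9 | 4.787 | 53.2% |

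With equal probability of each size: (1.833 + 3.367 + 4.787)/(3 + 6 + 9) = 9.987/18 = 55.5%. Simulated lists of 171 give 55.4% (95% of lists between 49.7% and 61.4%). That is about 95 correct guesses out of 171, against 57 by chance. Any mix of sizes lies between 53.2% and 61.1%.

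**Value of knowing the sizes.** An optimal guesser who knows the three sizes but not their order also scores 55.5%. The added knowledge makes about 3.7% of allocations certain.

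**What it could do to the F-test.** Assumptions, none of them from the protocol: no true arm effect, normal change with SD 3.9, and each patient lost with probability 0.2. A candidate's expected change is shifted by 1 or 2 points in the favourable direction when ALGO alone is behind, and in the unfavourable direction when ALGO is not among the smallest arms. Steering happens on every such occasion or on a quarter of them. Rounded over separate runs:

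| Steered share | 1 point | 2 points |
|---|---|---|
| All occasions | about 10% to 12% | about 31% to 34% |
| A quarter | about 5.5% | about 6% to 7% |

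Under constant steering ALGO appears about 0.65 or 1.3 points better. The definition of a predictable occasion matters. Counting ties for smallest gives about 15% and 41%. Counting only occasions when ALGO is alone at the bottom or alone at the top gives about 7% and 16%.

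**Alternatives on one list.**

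| Scheme | Guess rate |
|---|---|
| Blocks 6/9 | 54% |
| Blocks 9/12/15 | 51% |
| Blocks 12/15/18 | 50% |
| Arms allowed to differ by up to 6 | 37% |

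Under the last scheme, constant 2-point steering (ties counted) leaves type I error at about 5.5%. In 1,500 simulated lists no arm ended more than 4 patients from 57. With 42, 45 and 48 analysed, F-test power is 0.79 to 0.82, depending on which arm differs, against 0.805 at 45 each.

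**The case against.** The strongest reply is that randomly varied blocks behind a hidden list are ordinary practice, and that the harm depends on behaviour for which the protocol gives no sign.

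- **Steering is hard.** Referring GPs make the diagnosis and judge severity, so the investigator can only decline some of those referred. HAM-D6 is first rated at baseline, after randomisation, and the selector would have to predict change rather than severity. If screening judgement correlates 0.3 to 0.5 with later change (an assumption), a 1-point shift means turning away 31% to 54% of candidates on those occasions, and a 2-point shift 63% to 89%. This stands, and makes constant 2-point steering an upper bound.
- **Who sees what is inferred.** No section says that one person sees or tallies all allocations, and screening may be delegated. A single list is likewise inferred from the absence of strata. Both are the natural reading, but they are not stated.
- **Blocking has uses.** It balances arms over calendar time and serves the protocol's minimum of 57 per group. Simple randomisation of 171 would meet that minimum with a probability of only about 0.5%. This counts against unrestricted randomisation, but much less against a tolerance scheme.
- **Planned covariate models.** The exploratory models add baseline HAM-D6 and other variables, and could partly reveal or adjust for measured selection. The primary F-test is described without adjustment.

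Two stronger readings are tempting. A reader might infer that the F-test's true error rate is 17% or 52%. Those figures need no loss to follow-up and steering at nearly every non-tied allocation, roughly three quarters of enrolments. A reader might also infer that printing the block sizes is the main leak, but the guess rate is practically the same without knowing them.

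**Conclusion.** The point holds as a design weakness that should be corrected, not as an error that invalidates the trial. Hiding the list in REDCap does not prevent prediction from past allocations: the guess rate is about 55% instead of 33%, whatever the mix of sizes within 53% to 61%. This assumes one list and a team that can see past arms, both inferred.

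The figure measures opportunity. The documents do not support a claim that bias will occur. Occasional steering (a quarter of predictable occasions, 2 points) would raise type I error only to about 6% to 7%. Values of about 10% (1 point) to 34% (2 points) require constant steering, and they move with how a predictable occasion is defined.

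**What to change.** 1. For patients still to be randomised, load a new REDCap table from a restricted 1:1:1 scheme with a wide imbalance tolerance, for example arms allowed to differ by up to about 6. Keep the tolerance undisclosed. If blocks are retained, drop size 3 and use larger sizes; 9/12/15 is a partial gain only.
2. In the Randomisation section, replace the block sizes with a statement that details of the restriction are held in a document not available to those who enrol. On its own this removes only the roughly 4% of certain predictions.
3. Require eligibility to be recorded as final before the REDCap call. This leaves an audit trail and stops changes once the arm is known. It does not stop a decision made on a guess, so confirmation by someone unaware of past allocations is better where feasible.
4. Change the minimum of 57 per group to about 57.

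The cost is one allocation table and a few sentences. Final arm sizes may differ from 57 by a few patients, with negligible loss of power.

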## Measures and Outcomes

### Modified intention-to-treat (mITT) population and Per Protocol (PP) populations

The modified intention-to-Treat (mITT) population encompasses all randomised participants with at least one post-baseline HAM-D6 rating. The endpoint of the study is 12 weeks.

For participants with premature endpoints, the latest endpoint available will be used with last-observation-carried-forward (LOCF).

The Per Protocol (PP) populations are defined as completers at week 4 (PP4), at week 8 (PP8), or at week 12 (PP12).

### Primary outcome measure

The primary outcome measure is the Hamilton Rating Scale for Depression, 6 item version (HAM-D6), used as a continuous variable (20).

For all 3 arms an external rater will carry out the HAM-D6 screening.

### Secondary outcome measures

The following instruments will be used to assess the treatment course:

- The Columbia-Suicide Severity Rating Scale (C-SSRS) (21).
- The Major Depression Inventory (MDI) (22).
- The Personal and Social Performance Scale (PSP) (23).
- The Danish Adult Reading Test (DART) (24).
- The Brief INSPIRE-O (25).

### Primary outcome

The primary outcome of the study is the difference in HAM-D6 score from baseline to end of study at 12 weeks. It will be based on the mITT population.

### Secondary outcomes

All secondary outcomes are based on the mITT population unless otherwise specified. The following secondary outcomes will be explored:

- The difference in differences (DID) in HAM-D6 score, from baseline to end of study, between participants in:
  1. TAU-GP and ALGO
  2. TAU-GP-and TAU-P
  3. TAU-P and ALGO
- The DID in C-SSRS score, from baseline to end of study, between participants in:
  1. TAU-GP and ALGO
  2. TAU-GP-and TAU-P
  3. TAU-P and ALGO
- The DID in MDI score, from baseline to end of study, between participants in:
  1. TAU-GP and ALGO
  2. TAU-GP-and TAU-P
  3. TAU-P and ALGO
- The DID in PSP score, from baseline to end of study, between participants in:
  1. TAU-GP and ALGO
  2. TAU-GP-and TAU-P
  3. TAU-P and ALGO
- The impact of the assigned treatment pathway from the participant's point of view and the participant's personal experience of recovery through a self-rating scale (Brief INSPIRE-O). This will also be done using the DID, from baseline to end of study, between participants in:
  1. TAU-GP and ALGO

2. TAU-GP-and TAU-P

3. TAU-P and ALGO

- The concordance between MDI and HAM-D6.
- Duration of sick leave after baseline (indicated in days) within the current depressive episode.
- A Per Protocol analysis at week 12 (PP12) will also be completed for all continuous secondary outcomes.
- A Per Protocol analysis at week 12 (PP12) will also be completed for the primary outcome.
- Between-group difference for adverse events and serious adverse events.
- Between-group difference for the ITT population in reasons for premature discontinuation, time to all-cause discontinuation

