#### [Discontinuation criteria](#)

- Suicidality according to C-SSRS with a positive score to question 4 or 5 or upon the investigator's discretion.
- Severe somatic illness, as judged by the investigator.
- The patient wishes to stop participation and/or withdraws consent.
- The patient is unable to follow the treatment in one of the arms.
- Treatment will be terminated if the subject does not show up for two virtual meetings with the study staff or two meetings with the GP/psychologist, without cancelling, and

the study personnel are unable to get in contact with the participant. Attempts of contact are documented in the CRF.

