### [Withdrawal and dropout](#)

Withdrawal from the study will occur at the time when any of the discontinuation criterion are fulfilled, as judged by the investigator.

If possible, data regarding all outcome measures will be collected immediately or as soon as possible after the time of withdrawal. The primary outcome measure (HAM-D6) will have the highest priority. The primary reason for discontinuation will be recorded as well as the time of discontinuation. Subjects who have withdrawn will not be replaced.

If a study participant wishes to dropout, an interview regarding the reasons for dropping out will be offered to the patient concerned. The planned next rating session will be executed as soon as possible hereafter.

It is recommended that study participants discuss further treatment with the treating general practitioner responsible for their care.

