### [Completers](#)

Study participants will be defined as completers following the final visit at week 12 after baseline.

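### The completer (PP12) analysis of C-SSRS is selected on its own outcome, because a positive question 4 or 5 leads to withdrawal before week 12

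*Protocol*

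**What the plan says.** The relevant text is spread over several sections of the Protocol.

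- **Outcome.** Secondary outcomes lists "The DID in C-SSRS score, from baseline to end of study, between participants in" each of the three pairs of arms. C-SSRS is thus analysed as a change in score.
- **Populations.** The same section makes mITT the default for secondary outcomes and adds: "A Per Protocol analysis at week 12 (PP12) will also be completed for all continuous secondary outcomes". The Statistics section runs the difference-in-differences analysis in mITT with LOCF and in PP12. It also names C-SSRS among the scores analysed by mixed models in both populations.
- **Who is in PP12.** The population section defines it as week-12 completers, and the Completers section says: "Study participants will be defined as completers following the final visit at week 12 after baseline".
- **Who leaves.** Discontinuation criteria begins with "Suicidality according to C-SSRS with a positive score to question 4 or 5" or the investigator's discretion. Withdrawal and dropout adds: "Withdrawal from the study will occur at the time when any of the discontinuation criterion are fulfilled, as judged by the investigator".
- **Who enters.** Exclusion criteria bars patients on the same items: "Suicidality: according to C-SSRS with a positive response to question 4 or 5 within the last three months".
- **Related analyses.** Reasons for discontinuation and time to discontinuation are compared in the ITT population. Adverse events and serious adverse events are compared in mITT by Poisson regression with robust standard errors. Withdrawal and dropout asks for all outcome measures at or soon after withdrawal where possible, with HAM-D6 given priority.

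**The concern.** Ordinary dropout may be correlated with the outcome. Here the link is a rule: the answer that makes a C-SSRS result severe is also the answer that removes the patient from the completer set. The PP12 comparison then describes suicidality mainly among patients who did not become severely suicidal before the last visit.

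The trial compares pathways that begin with medication or with psychotherapy, so a between-arm comparison of suicidality will be read as safety information. If one arm has more withdrawals for suicidality at weeks 4 and 8, PP12 hides most of that excess and may look reassuring. A statistical analysis plan that followed the Protocol would inherit the problem, because the PP12 analysis is stated outright. The Protocol uses question 4 or 5 as its own threshold at entry and for withdrawal, but plans no comparison of the proportion of patients who cross it.

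**Working it through.** **The plan's own figures.** None is given for C-SSRS. The only sample-size figures are for HAM-D6: 45 per group, and 57 after 20% dropout. A one-way F-test with three groups, SD 3.9, alpha 0.05 and one arm 2.25 points from two equal arms gives power 0.805 at 45 per group. Then 45 / (1 − 0.20) = 56.25, rounded up to 57, and 3 × 57 = 171. These figures reproduce and are not in question. Only the arm size of 57 is used below.

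**Inputs from the Protocol.** Post-baseline C-SSRS at weeks 4, 8 and 12; withdrawal on a positive question 4 or 5; PP12 is those who have had the week-12 visit.

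**Assumptions.** A constant chance h per visit of a first positive answer, and withdrawal of every positive at the visit where it is found. The Protocol gives no rate, so a range is shown. Other dropout is ignored, so the expected counts are upper values for the given h.

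**Step 1: how many positives PP12 can contain.**

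- Any positive by week 12: 1 − (1 − h)³
- First positive at week 12, who can still be a completer: h(1 − h)²
- Share of positives that can remain: h(1 − h)² / [1 − (1 − h)³]

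| h per visit | Any positive by week 12 | First positive at week 12 | Share that can remain | Expected per arm of 57: all / in PP12 |
|---|---|---|---|---|
| 1% | 3.0% | 0.98% | 33% | 1.7 / 0.6 |
| 2% | 5.9% | 1.92% | 33% | 3.4 / 1.1 |
| 4% | 11.5% | 3.69% | 32% | 6.6 / 2.1 |

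About two thirds of positives are removed over this range. C-SSRS is also taken at the baseline visit, after randomisation at screening. If that visit is given the same chance h, the share that can remain falls to 23–25%.

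**Step 2: what happens to a difference between arms.** Take h = 1% in one arm and 3% in the other.

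- Any positive by week 12: 1 − 0.99³ = 2.97% and 1 − 0.97³ = 8.73%. The difference is 5.8 percentage points.
- Within PP12, patients positive at week 4 or 8 have gone, so the proportion positive is h itself: 1% and 3%. The difference is 2.0 points.

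With 2% against 4% per visit, the difference falls from 5.6 to 2.0 points. In both cases PP12 shows roughly one third of the difference.

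**Step 3: power of a direct comparison of proportions.** Two-sided 0.05, normal approximation, 57 per arm, assumed rates:

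- 2% against 6%: 19%
- 3% against 10%: 33%
- 5% against 15%: 43%

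Such a comparison would be descriptive.

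**The case against.** The strongest reply is that PP12 is not the trial's main look at suicidality. mITT is the default and PP12 is an addition. With LOCF, mITT can keep a severe value recorded at withdrawal. C-SSRS and HAM-D6 are scheduled together at weeks 4, 8 and 12 and at unscheduled visits, so a patient found positive at week 4 or 8 would normally have the post-baseline HAM-D6 that mITT requires. Withdrawals for suicidality also enter the ITT comparison of discontinuation reasons, and adverse events are compared separately. Most of this stands, and it is why the point is minor.

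Three gaps remain. A patient who is positive at the baseline visit and withdrawn before any post-baseline HAM-D6 is lost from mITT, and so from the adverse-event comparison too. The ITT comparison of reasons shows suicidality only as one reason among others, and it may miss a patient first positive at week 12 who has completed. And none of these analyses makes the PP12 result for C-SSRS interpretable.

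Three stronger readings are tempting but not supported:

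- **That PP12 must show no difference at all.** A patient first positive at week 12 has had the final visit and can be in PP12, and withdrawal rests on the investigator's judgement. The difference is attenuated, not erased.
- **That nearly all C-SSRS values lie at the floor.** The entry exclusion caps the baseline. It says nothing about how values are distributed below the cap, and the Protocol does not say which C-SSRS score is used.
- **That the mean-change t-test is an error.** One may prefer another summary, but nothing in the Protocol contradicts this one, and the score's definition may sit in a statistical analysis plan not seen here.

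**Conclusion.** The point holds for the PP12 analyses of C-SSRS, both the difference-in-differences test and the mixed model. They are selected on their own outcome by the Protocol's withdrawal rule, and the between-arm difference is biased toward no difference. Under a constant chance per visit, with every positive withdrawn when found, about one third of positives can remain, and a 5.8-point arm difference in positivity appears as about 2.0 points. Both the rates and the even timing are assumptions. If positives came earlier in one arm than in another, the distortion would differ. If the investigator kept some positive patients in the study, it would be smaller.

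A reader might infer that the trial has no usable comparison of suicidality. It does: the mITT analysis with LOCF and the ITT comparison of discontinuation reasons both contribute. Severity is low, because this is a supplementary analysis of a secondary outcome with no bearing on the primary outcome or the sample size.

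**What to change.** 1. In Secondary outcomes and Statistics, exempt C-SSRS from the PP12 analyses. Alternatively, keep them and label them as conditional on not having met the suicidality withdrawal criterion.
2. Keep the mITT analysis of C-SSRS as planned, including the mean-change comparison.
3. Add one binary outcome in all randomised patients: any positive answer to question 4 or 5 after randomisation, or withdrawal for suicidality, by week 12. Compare the arms with the robust Poisson regression already planned for categorical outcomes. State how patients with no C-SSRS after randomisation are counted.

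The cost is wording only. The assessments are already scheduled, the primary reason for discontinuation is already recorded, and the withdrawal rule is untouched. The downside is few events, hence wide confidence intervals, so the added comparison should be presented as descriptive.
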